Nicotine Dependence and Smoking Cessation. Tobacco use is the leading cause of preventable disease and death in the United States. Critically, the majority of smokers (70%) express a desire to quit smoking, but the vast minority of quit attempts (<5%) are successful long-term (> 3 months). Recent theories have proposed that failed quit attempts could in part be due to reward dysregulation in the brain that occurs with chronic drug use. Over time, repeated exposure to drugs of abuse increases subsequent reward responses to drugs and drug cues. Simultaneously, responses to non-drug rewards diminish, eventually failing to motivate behavior. This imbalance in drug versus non-drug reward responses may motivate the choice of drug stimuli over non-drug stimuli. If individuals can learn to increase the reward response to personalized, non-drug cues, it could motivate their future behavior towards non-drug stimuli. Likewise, by balancing out the reward responses to drug and non-drug cues, this may reduce the frequency and need for drug interactions, resulting in improved smoking cessation outcomes. The proposed personalized study in nicotine-dependent individuals has the potential to dramatically improve health outcomes and reduce health care cost nationwide. If successful, this protocol could readily be adapted for application to a variety of addictive disorders that act on the DA system including cocaine and other stimulants.

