Research on self-activation of the DA system is highly relevant to mental health. Several neurologic and psychiatric disorders are affiliated with abnormalities in the dopaminergic system, including addiction, depression, schizophrenia, and PD2-9. The predominant treatments for these disorders include pharmacotherapy and psychotherapy. However, a current barrier to progress in the field is that for many diseases neither treatment completely cures the disorder nor alleviates the symptoms. Furthermore, pharmacotherapy is associated with adverse side effects while psychotherapy is effortful, time intensive, costly, and - perhaps most challengingly - produces effects that are not immediately apparent. Therefore patients must persist for long periods of time (e.g., days to months) without any direct indication of progress. The NIMH Strategic Research Plan demands novel interventions that are personalized, safe, effective, and efficient. This research proposal investigates the development of cognitive neurostimulation of the dopaminergic midbrain as a personalized, safe, effective, and efficient micro-intervention for nicotine-dependent individuals.

The proposed studies address fundamental unsolved problems in behavioral science and systems neurobiology. Understanding if and how rt-fMRI and/or rt-EEG neurofeedback can enable individuals with and without nicotine dependence to activate the reward-related regions will advance clinical practice by offering a novel micro-intervention for patients with dysfunctional dopaminergic systems across disease etiologies.

Design & Procedures

We will enroll up to 150 adults between 18-45 years. We will recruit up to 100 adults with nicotine dependence and 50 adults without nicotine dependence. We may need to screen additional participants in order to achieve 150 completed participants (we estimate screening 250 participants).

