Delay to Smoking Assessment: for ND individuals, we may assess time (in minutes) that participants take to smoke their first cigarette (time and space permitting). After the MRI and/or EEG sessions we may give participants the opportunity to smoke a cigarette(s) if they would like. If we do the assessment, we will measure both the time it takes for them to take their smoking break as well as the number of cigarettes smoked. We may additionally collect self-report measures of craving.

Stimuli:

ReAcT Task: for the Activate trials in the ReAcT task, participants will be asked to provide approximately 50 pictures of personally rewarding objects or environments from their lives (e.g., family members, pets, favorite foods, favorite books, favorite places etc.). Participants will be asked to give the experimenter these electronic images (via the loaned camera or another method of their choice, e.g., thumbdrive) at least a few days prior to the fMRI session so that the experimenter can program them into the task. By doing so, the experimental task is personalized for each participant whereby they view their own personally rewarding images while they are inside the MRI machine or wearing the EEG headset. We believe this will elicit a much more realistic assessment of participant's reward sensitivity relative to generic images of rewarding items. These images will be stored on a secure server at Duke University. They will be labeled according to the de-identified participant number and will not be linked to any PHI. For the Count and Rest trials in the ReAcT task we will provide generic neutral and positive stimuli as control images.

Passive Viewing Task: In the passive viewing task participants will view the same images they provide for the ReAcT task. Adults who smoke will also view pictures of personalized smoking cues (e.g., cigarette of their choice, favorite place to smoke, etc.).

Reward Learning Task: in this task participants will view various neutral or positive images including shapes, objects, scenes, etc.

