Collection of psychophysiological data: In conjunction with fMRI data collection, physiological measures of heart rate and respiration may be recorded using an MR-safe commercial system (e.g., BIOPAC systems, Goleta, CA or the built-in GE equipment) to permit removal of physiological noise from the fMRI signal. This equipment is MR safe and has been used extensively at BIAC. Heart rate and respiration data will not be collected when using the EEG headset. Eye tracking data may also be collected. We may use the Tobii Pro eye tracker X2-60 (<https://www.tobiipro.com/product-listing/tobii-pro-x2-60/>), which is a screen-based eye tracker that sits on the computer. This eye tracker is not placed on the participant and therefore causes no physical discomfort and minimal disruption to the participant.

Questionnaire measures: The following self-assessment questionnaires may be completed at the Screening Visit. Note, the smoking related measures will only be collected for the smokers. Personal History Form, Personalized smoking history questionnaire, the Fagerström Test of Nicotine Dependence (FTND; 7 item), Center for Epidemiologic Studies Depression (CES-D; 20 item), the Temporal Experience of Pleasure Scale (18 item), Questionnaire of Smoking Urges-Brief (5 item), Contemplation Ladder (1 item), MNWS (8 item), SDSS (23 item), WISDM (37-item), Other tobacco use questionnaire (2 item), MTQ short form (48 item), the Snaith-Hamilton Pleasure Scale (SHAPS; 14 item), the Daily Experiences of Wanting and Liking (DEWL; 31 item), the General Self-Efficacy Scale (10 item), and the Multidimensional Personality Questionnaire Brief (MPQ; 155 items). We estimate that completion of these questionnaires will take approximately 45-60 minutes.

The following self-assessment questionnaires may be completed during the MRI or EEG Visit. Note, the smoking related measures will only be collected for the smokers. The Positive Affect Negative Affect

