To evaluate whether rt-fMRI neurofeedback improves the ability to increase reward-related brain activation in individuals with and without ND. To address this question we will compare individual's BOLD response to: baseline (passive viewing of reward images), Pre-Test (view personalized and non-personalized non-drug cues prior to neurofeedback), Training (view personalized, non-drug cues while receiving neurofeedback), and Post-Test (view personalized and non-personalized non-drug cues following neurofeedback). In this manner we will characterize and quantify individual's ability to increase brain activity to personalized, non-drug rewarding stimuli.

To examine the relationship between activation of reward-related regions via neurofeedback and dopamine availability (as assessed genetically). To assess this question we will first send the genetic data to the Duke University DNA Analysis Facility for analysis. Once the SNPs and VNTRs have been analyzed we will correlate individual's level of dopaminergic related genetic material (e.g., COMT, DAT) to their ability to regulate reward-related activation during the task.

To examine the effects of neurofeedback on clinically relevant outcomes, including reward responsivity and smoking related behaviors. To assess this we will examine participants brain activity during the Passive Viewing Task and the ReAcT. We will also perform a simple Delay to Smoking Assessment where we will measure (in minutes) how long participants take to smoke their first cigarette. We will also measure how many cigarettes they smoke during their break. We will correlate individual's ability to increase brain activation to personalized, non-drug cues in the ReAcT with both their time to initiate smoking and the number of cigarettes smoked.

Data & Safety Monitoring

Summarize safety concerns, and describe the methods to monitor research subjects and their data to ensure their safety, including who will monitor the data, and the frequency of such monitoring. If a data monitoring committee will be used, describe its operation, including stopping rules and frequency of review, and if it is independent of the sponsor (per 45 CFR 46.111(a) (6)).

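### The fourth aim asks what neurofeedback does to smoking, but its only stated analysis of smoking delay and cigarette count is an unadjusted correlation that can be positive with no training effect

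*Combined protocol and SAP*

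**What the plan says.** In Data Analysis & Statistical Considerations, the fourth aim is worded causally: "To examine the effects of neurofeedback on clinically relevant outcomes, including reward responsivity and smoking related behaviors". Brain activity in the Passive Viewing Task and the ReAcT is to be examined. For the post-session smoking measures, the single analysis given is: "We will correlate individual's ability to increase brain activation to personalized, non-drug cues in the ReAcT with both their time to initiate smoking". The sentence relates activation ability to "both their time to initiate smoking and the number of cigarettes smoked". It names no covariate, no group term and no significance level.

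Other parts of the document bear on this:

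- **Background, Nicotine Dependence and Smoking Cessation.** "Over time, repeated exposure to drugs of abuse increases subsequent reward responses to drugs and drug cues". The next sentence reads: "Simultaneously, responses to non-drug rewards diminish, eventually failing to motivate behavior". The resulting imbalance is then said to be a possible reason for choosing drug over non-drug stimuli.
- **Design & Procedures, ReAcT.** Participants may be randomised to Veridical Feedback or Noise Control. Both groups have a pre-test and a post-test.
- **Questionnaire measures.** The Fagerström scale is listed ("Test of Nicotine Dependence (FTND; 7 item"), among forms that may be completed at screening. No analysis uses it.
- **Selection of Subjects.** ND participants must report at least 5 cigarettes per day and have CO of at least 8 ppm. These are floors, so severity can vary widely above them.
- **Sample.** "We will recruit up to 100 adults with nicotine dependence and 50 adults without nicotine dependence". The delay measure is optional: "for ND individuals, we may assess time (in minutes) that participants take to smoke their first cigarette (time and space permitting".

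**The concern.** A correlation across people answers a different question from the one the aim poses. On the Background's account, a smoker with heavier exposure should respond less to non-drug images and may also be drawn to smoke sooner and more. Exposure, or severity as its proxy, then sits behind both variables. It produces a positive correlation of activation with delay, and a negative one with cigarette count, even if training did nothing. The same pattern could appear within the Noise Control group alone.

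What is at stake is interpretation. Under an aim about effects of neurofeedback, a significant correlation invites the reading that learning to activate these regions postpones smoking. It could equally mean that less dependent smokers have better preserved reward responses and smoke later. The planned analysis cannot tell these apart, although the plan already contains what would help: random assignment, a pre-test, the FTND and cigarettes per day.

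**Working it through.** **Plan's own figure.** None. The documents give no expected correlation, power or significance level for this aim, so there is nothing to reproduce.

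**Inputs from the documents.** At most 100 ND participants, with fewer likely to have delay data because the assessment is optional. The direction of the two links comes from the Background.

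**Assumptions.** Two-sided 5% test of a Pearson correlation by Fisher's z. Severity correlates −a with activation and −b with delay, with a = b from 0.2 to 0.6. Activation and delay have no other link, and there is no training effect.

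**Step 1: correlation produced by severity alone.** r = (−a)(−b) = a × b. At 0.3 each, r = 0.09.

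**Step 2: chance of a significant result.** With δ = atanh(r) × √(n − 3), the rejection probability is 1 − Φ(1.96 − δ) + Φ(−1.96 − δ). For r = 0.09 and n = 100, δ = 0.0902 × √97 = 0.89. The probability is 0.142 + 0.002 = 0.144.

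| a = b | r | n = 100 | n = 50 |
|---|---|---|---|
| 0.2 | 0.04 | 7% | 6% |
| 0.3 | 0.09 | 14% | 10% |
| 0.4 | 0.16 | 36% | 20% |
| 0.5 | 0.25 | 71% | 42% |
| 0.6 | 0.36 | 96% | 73% |

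A significant result becomes more likely than not when r reaches tanh(1.96/√(n − 3)). That is 0.196 at n = 100 and 0.278 at n = 50, which needs both links above √0.196 = 0.44 or √0.278 = 0.53. A simulation of 20,000 trials at n = 100 agrees with the formula: 14.8% at 0.3 and 71.1% at 0.5.

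**Step 3: if the score is a gain.** Write each run, in standardised units, as −aS plus a remainder, where S is severity. If S shifts both runs equally, post minus pre cancels −aS and nothing is left to correlate with delay. In simulation the mean r is 0.00 and the rejection rate 5.0%, at links of both 0.3 and 0.5.

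**Step 4: the remedies.**

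- Adjusting for perfectly measured severity brings rejection back to about 5% (simulated 4.8% to 5.2% with the level score).
- With a severity measure of reliability ρ (assumed) and a = b, the remaining partial correlation is a²(1 − ρ)/(1 − ρa²). For a = 0.5 and ρ = 0.8 this is 0.05/0.80 = 0.06, and 9% of trials reject. For ρ = 0.6 it is 0.10/0.85 = 0.12, and 21% reject.
- Comparing delay between randomised groups (1:1 assumed) holds about 5% in simulation without measuring severity.

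**The case against.** The strongest reply is that the activation score may already allow for the pre-test. Under the second aim, the plan compares passive viewing, pre-test, training and post-test, and says this comparison is how ability to increase activity will be quantified. The fourth aim uses almost the same phrase. A reader might infer from the bare correlation that the pre-test is ignored, but the documents do not support that. What they leave open is whether the correlated score is a level or a gain. If it is a gain and severity shifts both runs equally, Step 3 shows no bias. The Background describes a lower level of response, and does not say that heavier smokers gain less from training. This part of the reply stands. It narrows the concern without removing it, because the plan does not commit to such a score.

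A second reply is that the theory is weaker than a clean common cause. The Background speaks of chronic use and repeated exposure, not of severity among current smokers, and is tentative about drug choice. On its account, reduced non-drug response is itself part of the route to smoking. This also stands. It means that covariate adjustment alone would not isolate a training effect.

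Third, the numbers rest on assumed links, and 100 is a ceiling. This is true, and smaller samples lower the rejection rates. The difficulty of interpretation does not depend on sample size.

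**Conclusion.** The concern holds in a limited form. The unadjusted correlation cannot by itself show an effect of neurofeedback on smoking, and a positive result can arise without one.

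A reader might go further and infer that a positive result is to be expected without any training effect. The documents do not support this. They give a direction for the links but no size. At links of 0.3 with 100 participants, 86% of trials would show nothing significant.

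The inflation runs from about 7% to 96% over assumed links of 0.2 to 0.6 with a level score and n = 100, and is absent for a pure change score with a constant severity shift. The change is worth making because the mismatch between aim and analysis is plain from the text and the better analysis uses features already in the design.

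**What to change.** 1. Among randomised ND participants, make the comparison of Veridical Feedback with Noise Control on delay to smoking and on cigarette count the main smoking analysis of the fourth aim. It addresses the aim as worded and does not depend on measuring severity.
2. Keep the activation association as exploratory. Replace the correlation with a regression of each smoking measure on post-test activation, adjusted for pre-test activation, randomised group, FTND score and cigarettes per day at screening. This also settles the level-or-gain question. It remains observational, and Step 4 shows how much confounding an imperfect severity measure can leave.
3. In Questionnaire measures, change the FTND for ND participants at screening from optional to required.

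The cost is analysis wording, one 7-item form already on the list, and four degrees of freedom for the four adjusting terms in the exploratory model.

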Reward Activation Task (ReAcT): Participants may be randomly assigned to one of two groups. One group, the Veridical Feedback Group, will receive veridical neurofeedback from a reward related region, which may include the VTA, striatum, PFC, etc., while they are inside the MRI or while wearing the EEG headset. The other group, the Noise Control Group, will receive noise feedback that they are instructed is real or yoked sham feedback that is yoked to a participant's feedback in the Veridical Feedback Group. This group will serve as a critical control condition for the experiment. All participants will be debriefed in full about the study groups, random assignment, and the purpose of each group in contributing to our understanding of the reward-related brain regions' role in reward processing in individuals with and without ND.

Participants may complete the ReAcT. The ReAcT consists of two types of runs: test runs (one pre-test and one post-test) and training runs (see Fig. 1 for a sample task design). For both groups the pre-test measures baseline reward-related brain activation prior to receiving rt-fMRI or EEG neurofeedback. For

the Veridical Feedback Group, the training runs train participants to use rt-fMRI or EEG neurofeedback to more efficiently and successfully increase their brain activity. For the Noise Control Group, the training runs serve as a control wherein they continue to try to increase brain activity. For all participants, the post-test measures if participants are better able to activate the brain after training.

Test runs: For both Groups the pre and post-test runs are identical and contain two or three trial types: Activate, Count, and Rest. During Activate trials participants will try to increase reward feelings to personalized images of rewarding items (e.g., favorite food, picture of a pet; see Fig. 1). During Count trials participants will count backwards, providing a standardized period for all participants. During Rest trials, participants are instructed to either not think of anything in particular or to view and think about an image shown to them (neutral-positive image). The test runs will have 5-7 repetitions of each trial, separated by a jittered inter-trial-interval (ITI).

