If anxiety rating is still 7 or higher, do another round of 10 breaths of deep breathing and reassess anxiety. If anxiety rating has not reduced after that, escort the participant to the Duke Emergency Department.

If anxiety rating is reduced and participant is reporting an increasing sense of control over his/her anxiety, proceed to the Relaxation Protocol, below.

Relaxation Protocol

Escort the participant to a room outside the testing environment where a comfortable chair is available.

Ask the participant to sit down, and say,

I would like you to listen to this tape and follow the instructions. It will be guiding you through some relaxation exercises. It will take approximately ten minutes to complete the tape. I'll come back to check on you when you're done. Start the progressive muscle relaxation tape. When the tape is finished, assess the participant's anxiety level a final time.

Anxiety Rating: _____

In control? YES | NO

Provide professional referral resources as needed.

[name] who is psychiatrist will be on call during all scanning sessions.

Adverse Event and Serious Adverse Event reporting: Adverse events are recorded in an Adverse Event Log and reported annually to the IRB via the Continuing Renewal Process. In Accord with the IRB, AEs are considered SAEs, if they are serious, unexpected, and related to the protocol. We will report SAEs to the IRB within 1 week of occurrence.

Data Analysis & Statistical Considerations

Behavioral, EEG, and genetic data will be analyzed using statistical software including MATLAB, R, Python, and SPSS. The genetic information will be sent to the Duke University DNA Analysis Center for analysis. Imaging data will be analyzed using commercially available programs including Python, MATLAB, and FSL.

For the fMRI data, following data collection, the time series of activation within the VTA107,125 will be extracted for each participant. Primary analyses on these data will be conducted on a within and between-subject basis as follows:

To assess the ability of adults with and without ND to activate reward-related brain areas (e.g., VTA, striatum, PFC). To address this question we will extract time courses from the target areas and examine the brain response (BOLD signal) to personalized and non-personalized drug and non-drug cues.

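### The fourth aim asks for the effect of neurofeedback on smoking, but the only analysis stated for the two smoking outcomes is a correlation with activation ability, and delay has no rule for participants who do not smoke

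*Combined protocol and SAP*

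**What the plan says.** The fourth aim appears under Purpose of the Study and again under Data Analysis & Statistical Considerations, where it reads "To examine the effects of neurofeedback on clinically relevant outcomes, including reward responsivity and smoking related behaviors". Under it, the analysis section says that brain activity in the Passive Viewing Task and the ReAcT will be examined, and that minutes to the first cigarette and the number of cigarettes smoked in the break will be measured. The only analysis given for those two measures is a correlation of each individual's "ability to increase brain activation to personalized, non-drug cues in the ReAcT with both their time to initiate smoking", and with the cigarette count.

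The ReAcT section says "Participants may be randomly assigned to one of two groups" (Veridical Feedback or Noise Control) and says of the second: "This group will serve as a critical control condition for the experiment". The analysis section names neither group. Its one general sentence on comparisons, which follows a reference to the fMRI data, is "Primary analyses on these data will be conducted on a within and between-subject basis as follows".

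The activation measure seems to come from the second aim, which compares baseline, Pre-Test, Training and Post-Test and concludes "In this manner we will characterize and quantify individual's ability to increase brain activity to personalized, non-drug rewarding stimuli". No single score is defined.

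The Delay to Smoking Assessment section makes smoking voluntary: "we may give participants the opportunity to smoke a cigarette(s) if they would like". It gives no maximum observation time and no value for a participant who does not smoke.

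**The concern.** The aim names a causal effect and the design describes the randomised contrast that could estimate it. The stated analysis instead relates smoking to a variable measured after assignment. People who raise activation more may differ from others in motivation, dependence or reward sensitivity, and those traits may also govern how soon they smoke. A correlation can therefore appear with no effect of feedback on smoking, and its size does not reveal the effect when there is one. A team could follow the plan to the letter and never report the smoking effect that the aim promises.

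The second gap concerns delay only. Minutes to first cigarette are not observed for a participant who does not smoke, and those are plausibly the people with the longest delays. Leaving them out, capping them and censoring them are all compatible with the text. The cigarette count has no such problem, since not smoking is a count of zero.

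**Working it through.** The plan states no alpha, power, effect size or allocation ratio, and no number randomised, assessed or not smoking, so it has no figure to reproduce. The one document input is the ceiling of 100 participants with nicotine dependence (Design & Procedures). Everything else is assumed, with two-sided alpha 0.05.

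**1. What a given correlation says about the arm effect.** Let activation = d × arm + noise (within-arm SD 1) and delay = b × activation + noise (within-arm SD 1), with 1:1 allocation and feedback acting on delay only through activation. The pooled correlation is r = b√(1 + d²/4) / √(1 + b²d²/4). Solving gives b = r / √(1 + (1 − r²)d²/4), and the arm difference in delay is b × d.

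| Pooled r | d = 0 | d = 0.5 | d = 0.8 |
|---|---|---|---|
| 0.30 | b = 0.300, difference 0 | b = 0.292, difference 0.15 SD | b = 0.280, difference 0.22 SD |
| 0.40 | b = 0.400, difference 0 | b = 0.390, difference 0.20 SD | b = 0.376, difference 0.30 SD |

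One correlation thus fits differences from 0 to 0.30 SD, depending on how far feedback moves activation. This holds whether the activation score is a level or a change.

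**2. A correlation with no arm effect on smoking.** Simulation with 50 per arm: feedback raises activation by 0.5 SD and does nothing to smoking, and a shared trait explains a fraction a of the variance of each measure. The expected pooled r is a / √(1 + 0.5²/4); for a = 0.3 this is 0.3 / √1.0625 = 0.29. The correlation is significant in 16%, 85% and over 99% of trials for a = 0.1, 0.3 and 0.5. The arm comparison rejects in about 5% throughout, as it should.

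**3. Participants who do not smoke, in the planned correlation with delay.** Simulation (3,000 trials per cell) with Spearman correlation, latent r = 0.4 and n = 100; those who do not smoke are the longest latent delays.

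| Not smoking | Left out: mean rho, power | Kept as tied longest: mean rho, power |
|---|---|---|
| 5% | 0.35, 95% | 0.38, 98% |
| 10% | 0.33, 89% | 0.38, 98% |
| 20% | 0.30, 78% | 0.38, 97% |

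With n = 60, power is 78%, 69% and 53% when they are left out, against 84 to 86% when they are kept. With a true correlation of zero, both handlings reject in about 5% of trials.

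**4. Precision of an arm comparison.** The Schoenfeld formula at 1:1 gives power = Φ(√(events)/2 × |ln HR| − 1.96). At an assumed HR of 0.6, |ln HR| = 0.511.
- 100 events: Φ(5 × 0.511 − 1.96) = Φ(0.59) = 72%.
- 60 events: Φ(3.873 × 0.511 − 1.96) = Φ(0.02) = 51%.
- The 95% interval is the estimate multiplied and divided by exp(1.96 × 2/√events): 1.48 with 100 events, 1.66 with 60.

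If the effect runs only through activation (d = 0.5 to 0.8, b = 0.3 to 0.4), a t-test on delay has power of 11 to 35% with 50 per arm and 9 to 23% with 30 per arm.

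**The case against.** The correlation fits the rationale in Background & Significance, where learning to raise the response to non-drug cues is what should change behaviour. That stands: it is a sensible mechanistic analysis and should stay.

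The within and between-subject sentence might be read as covering a group comparison. Its scope is ambiguous, because it follows a reference to the fMRI data but introduces all four aims. Even on the widest reading it defines no Veridical versus Noise Control contrast for any outcome.

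Random assignment is worded as something that may happen, and the smoking assessment depends on time and space. The point is therefore limited to participants with nicotine dependence who were randomised and assessed. The smoking measures are also only part of the last-listed aim, and an arm comparison may give a wide interval. Both objections are fair and bear on how the result is reported. Low power does not turn the correlation into an estimate of the effect.

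A reader might go further and infer that the plan drops participants who do not smoke, or that this would produce false findings. The documents do not say that they are dropped, nor how many there will be. In the case simulated, leaving them out weakened a real correlation but left the false-positive rate at about 5%.

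**Conclusion.** The point holds. As written, the plan yields no estimate of the effect of veridical feedback on time to first cigarette or cigarette count, although the aim names that effect and a control group is described. It should be fixed; it does not undermine the study's other analyses.

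On size, a pooled correlation of 0.30 to 0.40 leaves an arm difference between 0 and 0.30 SD open under full mediation, and a shared trait can produce a correlation with no arm effect at all. A reader might infer that a sizeable effect on smoking is being hidden; these figures show only that zero to fairly small differences cannot be told apart. For delay, the missing rule costs little at 5% not smoking (power 95% against 98%) and more at 20% (78% against 97%). Every figure rests on assumed inputs, and none is an estimate of bias in this trial.

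**What to change.** Among participants with nicotine dependence who were randomised and had the Delay to Smoking Assessment:

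- Add a Veridical versus Noise Control comparison for both smoking outcomes, each reported as an estimate with a 95% confidence interval, with the numbers assessed and smoking in each arm.
- Record an end of observation for each assessed participant. Keep those who do not smoke in the delay analysis, either censored (log-rank or Cox) or tied longest (a rank test on capped times), and count them as zero cigarettes.
- Keep the activation-smoking correlation as a mechanistic analysis, within or adjusted for arm, using one stated activation score and retaining participants who do not smoke.
- If the arm comparison is not added, reword the smoking part of the aim as an association.

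Two points of wording can be settled at the same time. The design section says the assessment may be done and the analysis section says it will be. The design section also says "If we do the assessment, we will measure both the time it takes for them to take their smoking break", whereas the analysis section times the first cigarette; the start and the event should be stated once.

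The cost is SAP wording and a small burden in recording an end time. The main drawback is modest power: about 72% with 100 events and 51% with 60 at an assumed HR of 0.6 and 1:1 allocation, and about 11 to 35% with 50 per arm if the effect runs only through activation. The result should therefore be read as an estimate with its interval, beside the correlation.
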